5.2.1 BCG Treatment

5.2.1.1 BCG treatment will be according to Institutional standard for the site; however, the BCG will be provided by MERCK due to the BCG shortage to ensure completion of the study.

For patients with multi-focal disease, it is highly recommended that the patient have a urologic stent and catheter placed prior to the first pembrolizumab treatment to allow for stabilization of the mucosa prior to the start of treatment with BCG. Placement will be at the discretion of the treating physician.

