5.4 Rescue Medications & Supportive Care

5.4.1 Supportive Care Guidelines

Subjects should receive appropriate supportive care measures as deemed necessary by the treating investigator. Suggested supportive care measures for the management of adverse events with potential immunologic etiology are outlined below. Where appropriate, these guidelines include the use of oral or intravenous treatment with corticosteroids as well as additional anti-inflammatory agents if symptoms do not improve with administration of corticosteroids. Note that several courses of steroid tapering may be necessary as symptoms may worsen when the steroid dose is decreased. For each disorder, attempts should be made to rule out other causes such as metastatic disease or bacterial or viral infection, which might require additional supportive care. The treatment guidelines are intended to be applied when the Investigator determines the events to be related to pembrolizumab.

Note: If after the evaluation the event is determined not to be related, the Investigator does not need to follow the treatment guidance (as outlined below). Refer to Section 5.2.1 for dose modification.

It may be necessary to perform conditional procedures such as bronchoscopy, endoscopy, or skin photography as part of evaluation of the event.

- **Pneumonitis:**

- For **Grade 2 events**, treat with systemic corticosteroids. When symptoms improve to Grade 1 or less, steroid taper should be started and continued over no less than 4 weeks.
- For **Grade 3-4 events**, immediately treat with intravenous steroids. Administer additional anti-inflammatory measures, as needed.
- Add prophylactic antibiotics for opportunistic infections in the case of prolonged steroid administration.

- **Diarrhea/Colitis:**

Subjects should be carefully monitored for signs and symptoms of enterocolitis (such as diarrhea, abdominal pain, blood or mucus in stool, with or without fever) and of bowel perforation (such as peritoneal signs and ileus).

- All subjects who experience diarrhea/colitis should be advised to drink liberal quantities of clear fluids. If sufficient oral fluid intake is not feasible, fluid and electrolytes should be substituted via IV infusion. For Grade 2 or higher diarrhea, consider GI consultation and endoscopy to confirm or rule out colitis.
- For **Grade 2 diarrhea/colitis**, administer oral corticosteroids.

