8.1.2.2 Adverse Event (AE) Monitoring

The Investigator or qualified designee will assess each subject to evaluate for potential new or worsening AEs as specified in the Trial Flow Chart and more frequently, if clinically indicated. Adverse experiences will be graded and recorded throughout the study and during the follow-up period according to NCI CTCAE Version 4.0 (Appendix E). Toxicities will be characterized in terms regarding seriousness, causality, toxicity grading, and action taken with regard to trial treatment. AEs will be recorded from the time the subject signs the consent through 30 days post the last study treatment.

Please refer to section 9.0 for detailed information regarding the assessment and recording of AEs.

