	Is a new cancer ; (that is not a condition of the study) or (although not serious per ICH definition, is reportable to the Sponsor within 24 hours and to Merck within 2 working days to meet certain local requirements); or	
	Is an overdose (whether accidental or intentional). Any adverse event associated with an overdose is considered a serious adverse event, for collection purposes. An overdose that is not associated with an adverse event is considered a non-serious event of clinical interest and must be reported within 24 hours to the Sponsor and to Merck within 2 working days.	
	Other important medical events that may not result in death, not be life threatening, or not require hospitalization may be considered a serious adverse event when, based upon appropriate medical judgment, the event may jeopardize the subject and may require medical or surgical intervention to prevent one of the outcomes listed previously (designated above by a †).	
Duration	Record the start and stop dates of the adverse event. If less than 1 day, indicate the appropriate length of time and units	
Action taken	Did the adverse event cause Merck product to be discontinued?	
Relationship Merck Product	Did the product cause the adverse event? The determination of the likelihood that Merck product caused the adverse event will be provided by an Investigator who is a qualified physician. The investigator’s signed/dated initials on the source document or worksheet that supports the causality noted on the AE form, ensures that a medically qualified assessment of causality was done. This initialed document must be retained for the required regulatory time frame. The criteria below are intended as reference guidelines to assist the Investigator in assessing the likelihood of a relationship between the test drug and the adverse event based upon the available information. The following components are to be used to assess the relationship between Merck product and the AE ; the greater the correlation with the components and their respective elements (in number and/or intensity), the more likely Merck product caused the adverse event (AE):	
	Exposure	Is there evidence that the subject was actually exposed to the product such as: reliable history, acceptable compliance assessment (pill count, diary, etc.), expected pharmacologic effect, or measurement of drug/metabolite in bodily specimen?

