	Time Course	Did the AE follow in a reasonable temporal sequence from administration of Merck product? Is the time of onset of the AE compatible with a drug-induced effect (applies to trials with investigational medicinal product)?

	Likely Cause	Is the AE not reasonably explained by another etiology such as underlying disease, other drug(s)/vaccine(s), or other host or environmental factors
--	---------------------	---

Relationship to Merck Product (continued)	The following components are to be used to assess the relationship between the test drug and the AE: (continued)	
	Dechallenge	Was Merck product discontinued or dose/exposure/frequency reduced? If yes, did the AE resolve or improve? If yes, this is a positive dechallenge. If no, this is a negative dechallenge. (Note: This criterion is not applicable if: (1) the AE resulted in death or permanent disability; (2) the AE resolved/improved despite continuation of the Sponsor's product; or (3) the trial is a single-dose drug trial; or (4) Sponsor's product(s) is/are only used one time.)
	Rechallenge	Was the subject re-exposed to the product in this study? If yes, did the AE recur or worsen? If yes, this is a positive rechallenge. If no, this is a negative rechallenge. (Note: This criterion is not applicable if: (1) the initial AE resulted in death or permanent disability, or (2) the trial is a single-dose drug trial); or (3) Sponsor's product(s) is/are used only one time). NOTE: IF A RECHALLENGE IS PLANNED FOR AN ADVERSE EVENT WHICH WAS SERIOUS AND WHICH MAY HAVE BEEN CAUSED BY THE PRODUCT, OR IF REEXPOSURE TO MERCK PRODUCT POSES ADDITIONAL POTENTIAL SIGNIFICANT RISK TO THE SUBJECT, THEN THE RECHALLENGE MUST BE APPROVED IN ADVANCE BY THE SPONSOR AS PER DOSE MODIFICATION GUIDELINES IN THE PROTOCOL.
	Consistency with Trial Treatment Profile	Is the clinical/pathological presentation of the AE consistent with previous knowledge regarding Merck product or drug class pharmacology or toxicology?
The assessment of relationship will be reported on the case report forms /worksheets by an Investigator who is a qualified physician according to his/her best clinical judgment, including consideration of the above elements.		
Record one of the following		Use the following scale of criteria as guidance (not all criteria must be present to be indicative of a product relationship).

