Yes, there is a reasonable possibility of product relationship.		There is evidence of exposure to Merck product. The temporal sequence of the AE onset relative to the administration of Merck product is reasonable. The AE is more likely explained by Merck product than by another cause.
No, there is not a reasonable possibility of Merck product relationship		Subject did not receive the product OR temporal sequence of the AE onset relative to administration of Merck product is not reasonable OR the AE is more likely explained by another cause than the Merck product. (Also entered for a subject with overdose without an associated AE.)

Product: MK-3475

Protocol/Amendment No.: Amendment 5, 21 October 2019

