11.0 LABELING, PACKAGING, STORAGE AND RETURN OF CLINICAL SUPPLIES

11.1 Standard Treatment

BCG will be utilized as the product of standard treatment for this protocol for superficial bladder cancer. The Investigator will take appropriate steps to ensure that appropriate records are maintained regarding the use of BCG in the study. BCG will be supplied through commercial sources and the supply, storage, handling, distribution, and usage of BCG will be in accordance with local practice and any applicable laws and regulations, including this protocol.

Clinical Supplies will be provided through commercial sources. The approved package labeling will be utilized for the preparation and storage and handling of BCG.

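### Table 8 records causality and action only for an undefined Merck product, so a BCG-type toxicity to which MK-3475 contributed may be coded unrelated

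*Combined protocol and SAP*

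**What the plan says.** Section 3.1 makes the safety of MK-3475 given with intravesical BCG the primary objective. Section 8.1.2.2 says toxicities will be described by "seriousness, causality, toxicity grading, and action taken with regard to trial treatment". Table 8 in section 9.1.4 is where that assessment is set out:

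- **Causality.** One question, about one product: "The determination of the likelihood that Merck product caused the adverse event will be provided by an Investigator who is a qualified physician".
- **Competing causes.** The likely-cause component begins "Is the AE not reasonably explained by another etiology such as underlying disease, other drug(s)/vaccine(s" and continues with host and environmental factors.
- **Answers.** There are two. Yes is described by exposure, reasonable timing, and the Merck product being the likelier explanation. No is supported by any one of non-exposure, unreasonable timing, "OR the AE is more likely explained by another cause than the Merck product".
- **Action taken.** The whole item is "Did the adverse event cause Merck product to be discontinued".

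Table 8 presents these criteria as guidance and leaves the final answer to the physician's judgement.

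The term Merck product is not defined. Section 5.2.1.1 says "the BCG will be provided by MERCK due to the BCG shortage", while section 11.1 says "BCG will be supplied through commercial sources". The text under Table 2 in section 5.2 also describes commercial supply, and section 5.2.1.1.2 allows BCG from other manufacturers.

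**The concern.** In a combination-safety trial, the event of most interest is a toxicity of one agent made worse by the other. Table 8 has no place for it. If Merck product means MK-3475, BCG is one of the other drugs, and a reaction that follows an instillation meets the description of a No whenever BCG is the likelier explanation, even if MK-3475 plausibly added to it. Nothing in the table records that BCG was judged responsible, that both agents were, or that either agent was held rather than stopped.

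Several rules elsewhere turn on a relatedness judgement. If investigators take that judgement from Table 8, a No entered because BCG seemed likelier could carry into MK-3475 holds, the dose-escalation count and the use of the immune-toxicity guidance.

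**Working it through.** No figure in the plan needs reproducing. The check sets the texts side by side and then sizes the overlap.

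**1. Table 8 against section 8.1.2.2.** The section covers trial treatment, which is MK-3475 and BCG. Table 8 covers one product, and for action only discontinuation. Section 5.2.4, however, acts on holds of either drug lasting more than 2 weeks because of toxicity. So Table 8 does not deliver what section 8.1.2.2 describes.

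**2. Label against criterion.** The two answers are labelled by whether a relationship is reasonably possible. The criteria beneath them ask which cause is more likely. A BCG reaction to which MK-3475 contributed can satisfy the Yes label and the No criterion at once.

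**3. The two readings of Merck product.** If it means MK-3475 alone, as the single-agent wording elsewhere in Table 8 (test drug, Sponsor's product) suggests, BCG attribution is not collected there. If it includes BCG because Merck supplies it, a BCG reaction is coded Yes, but the agents cannot be told apart and the answer cannot inform a rule specific to MK-3475. Neither reading gives attribution by agent.

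**4. Where relatedness is used.**

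| Place | Depends on relatedness? |
|---|---|
| Section 10.1, adverse events by grade | No |
| Section 6.1, data shown to the review team | No |
| Section 5.8, grade 4 counts (1, 4 and 5 subjects) | No condition stated |
| Section 9.1.3.1, SAEs up to 90 days after treatment (30 if new anticancer therapy starts) | No |
| Section 5.8, fatal or morbidity trigger | Yes, on study treatment or procedures; Table 8 has no such item |
| Table 3, MK-3475 holds and discontinuations | Largely yes (drug-related); its introduction also names severe and life-threatening events |
| Escalation count (5.2.3.1, 5.8, 6.1, 8.1.6.2.1) | Indirectly, through MK-3475 holds and discontinuations |
| Section 5.4.1 | Yes: "The treatment guidelines are intended to be applied when the Investigator determines the events to be related to pembrolizumab" |
| Section 5.2.1.1.3, BCG holds | Only for Grade 4 haematologic toxicity, with the drug not named |
| Section 9.1.3.1, SAEs after the window | Yes, on the investigational product |

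**5. Size of the overlap.** Inputs: 15 subjects (section 2.1), escalation cohorts of 3 or 6 (section 5.2.3.1), and BCG effect frequencies (section 5.2.1.4). Hepatitis and pneumonitis overlap the liver-test and pneumonitis rows of Table 3, and both are listed below 4%. Expected cases of each = rate × n:

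- first 3 subjects: below 0.04 × 3 = 0.12
- 6 subjects: below 0.04 × 6 = 0.24
- all 15 subjects: below 0.04 × 15 = 0.6

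Five effects (dysuria, frequency, flu-like symptoms, haematuria, fever) are listed at 20% or more: at least 0.20 × 15 = 3 subjects each. None is a named Table 3 row. They could enter through its catch-all row, mainly at Grade 3 or above, and the documents give no rate for that.

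**6. Sensitivity of the escalation count.** The rule changes outcome at one and at two subjects: none of three, one of three (expand to six), two of three or two of six (no escalation). One attribution can therefore move the count across a boundary. All six instillations fall in weeks 7-12, within 2 of the 6 MK-3475 cycles (section 8.1.2), which is when attribution is hardest.

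**The case against.** The strongest reply is that little of the safety evaluation passes through Table 8. Step 4 bears this out for the primary table, the review team's data, the grade 4 counts and in-window SAE reporting. Fever and haematuria lead to a BCG hold at the stated grades whatever the causality code. Section 5.4.1 merely releases the investigator from its guidance when an event is judged unrelated; it does not forbid its use. No text says that drug-related in Table 3 is read from the Table 8 code. All of this stands, and it limits the point.

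Three stronger readings are tempting, and the documents do not support them:

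- A reader might infer that a BCG toxicity worsened by MK-3475 will be coded unrelated. The criteria are guidance, and the Yes label asks only for a reasonable possibility, so a physician may code Yes. If Merck product includes BCG, Yes would be the expected answer.
- A reader might infer that related-event rates will be biased low. The SAP plans no related-event table. The 3 of 15 figure is a listed BCG side-effect frequency, not an estimate of misclassification.
- A reader might infer that toxicities which stopped BCG cannot be tabulated. The adverse-event CRF is not among the documents, and section 8.1.2.2 does ask for action on trial treatment.

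It is also fair to say that, with one arm and no BCG-alone control, aggravation is hard to establish for a single event. That argues against a separate combination item, but not against recording each agent. The reply does not remove the mismatch between Table 8 and section 8.1.2.2, the undefined term, or the exposure of the rules that do use relatedness.

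**Conclusion.** The point holds in limited form. Table 8 collects causality and discontinuation for one undefined product, supports a No when another cause is merely likelier, and has no BCG attribution and no record of holds. A toxicity to which both agents contributed may be coded unrelated.

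The exposure is confined to relatedness coding, Table 3 holds that turn on drug-relatedness and through them the escalation count, the section 5.4.1 guidance, the study-treatment trigger in section 5.8, and SAE reporting after the window. By the listed BCG frequencies, the named overlaps would be few: under 0.6 cases each of hepatitis and pneumonitis in 15 subjects. One case could nevertheless matter in a cohort of three or six.

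This rests on four assumptions: Merck product means MK-3475; investigators carry the Table 8 judgement into the rules that use relatedness; the CRF mirrors Table 8; and the listed BCG frequencies apply here. The rate under the combination is unknown. The change is worth making, but the primary adverse-event summary does not depend on it.

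**What to change.** 1. Define Merck product in section 9.1.4, or replace it with the agent's name.
2. In Table 8 and the adverse-event CRF, record relationship (reasonable possibility, yes or no) separately for MK-3475 and for BCG. Allow Yes to both, so that a joint contribution is captured.
3. Record action taken separately for each agent, distinguishing held from discontinued.
4. Reconcile Table 8 with section 8.1.2.2 and with the relatedness wording in sections 5.2.1.1.3 and 5.8 and in Table 3, so that it is clear which recorded item each rule refers to.
5. Reconcile the BCG supply statements in sections 5.2, 5.2.1.1 and 11.1.

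No hold, stopping or escalation rule should change as part of this. In particular, the fix should not put a new definition into the section 5.8 stopping rules. Nor should it bar BCG outright as another cause, because an ordinary BCG reaction could then not be coded unrelated to MK-3475 on that ground.

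The cost is a few CRF fields and short edits to the text. More events may be recorded as related.

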9.1.5 Sponsor Responsibility for Reporting Adverse Events

All Adverse Events will be reported to regulatory authorities, IRB/IECs and Investigators in accordance with all applicable global laws and regulations. If appropriate, adverse events will be reported to the drug manufacturer's safety division.

10.0 STATISTICAL ANALYSIS PLAN

10.1 Statistical Analysis Plan Summary

A minimum of 15 subjects will be enrolled. Seventy percent of bladder tumors are superficial [22] indicating to enroll at least 15 patients, approximately 21-25 patients will need to be approached to meet eligibility and to allow for patient disinterest.

Fifty percent of those patients who respond to BCG treatment develop recurrent disease [30; 31] generally detected within 6 months of BCG treatment. Those patients with recurrent disease often are sent for radical cystectomy as there are no other acceptable standard treatment options. This study, though primarily evaluating maximum tolerated dose, will examine the percent response at 19 weeks to determine if MK-3475 has altered the pattern of responders as early as 19 weeks from the start of treatment. The results of this study will not only examine the safety of combining MK-3475 with BCG for future studies, but will also assist in determining patient eligibility (recurrent superficial bladder cancer versus initial diagnosis) and considerations for future study design.

Patient related data will be collected and transferred to an excel spreadsheet for statistical analysis. SAS software version 9.4 will be used for all data analysis. Descriptive statistics will be computed for all study variables. Continuous variables will be described with measures of central tendency (mean, median) and dispersion (range, standard deviation). Categorical variables will be summarized as frequencies and percentages. Some examples include tumor stage (Ta, T1, Cis), age, ECOG Performance Scale (0, 1, 2), sex, and use of tobacco and alcohol.

For primary objective 1, the proportion of patients with each AE will be reported along with the NCI CTCAE Grade of the AE. The Quality of Life Questionnaire, which includes one question with seven categorical responses, will be described with frequencies and percentages. The American Urologic Association Symptoms Index Questionnaire, which includes seven questions each with a numerical score between 0 and 5 as well as a final numerical sum of all responses, will be described with measures of central tendency and dispersion. Due to the questionnaires being given at three time points (Pre-treatment, Mid-treatment, and Post-treatment), the responses may be analyzed to look for longitudinal effects over time for specific variables of interest with repeated measures ANOVA to evaluate changes and control for individual differences (*although this would be very low power due to n=15*).

For the secondary objective, subjects will be assessed at 19 weeks, 3 months, 12 months, and 24 months post treatment completion for complete response. The outcome endpoint will be complete response status at 19 weeks, 3 months, 12 months, and 24 months post treatment to measure complete response, recorded as yes or no and summarized as proportions and a percent.

Product: MK-3475

Protocol/Amendment No.: Amendment 5, 21 October 2019

These proportions/percent will be reported, but no statistical analysis will be performed as this is a single arm phase I study, and no control group is available for direct comparison.

For the exploratory objectives, Pearson or Spearman's rank correlation coefficient will be used to estimate correlations between expression level change and treatment outcome, as well as the correlations between mutation presence and treatment outcome.

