8.1.2 Clinical Procedures/Assessments

Subjects diagnosed with T1 and Ta tumors require restaging after failure of BCG and one course of maintenance or failure after BCG plus one of the following: mitomycin, gemcitabine, or BCG/interferon. Subjects receiving bladder tumor resection at outside institutions are eligible for the study; however, pathology slides must be reviewed by the site’s pathology department. Each subject will receive a total of 6 cycles of treatment with MK-3475 at a dose of 100 (first 3 subjects) or 200 mg on Day 1 of a 21 day cycle. Two cycles of MK-3475 will occur prior to BCG intravesical treatment (weekly doses for 6 weeks) with concurrent treatment (MK-3475 and BCG) starting on cycle 3 and ending the third week of cycle 4. MK-3475 will then be continued as a single agent for 2 additional cycles after the last dose of BCG was administered.

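### Table 8 gives no way to attribute an adverse event to BCG, and Section 10.1 does not plan to show when events arose relative to BCG

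*Combined protocol and SAP*

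**What the plan says.** - **Objective.** Section 3.1 asks whether MK-3475 can be given safely in combination with BCG.
- **Schedule.** Section 8.1.2: "Each subject will receive a total of 6 cycles of treatment with MK-3475", each of 21 days. "Two cycles of MK-3475 will occur prior to BCG intravesical treatment"; concurrent dosing runs "starting on cycle 3 and ending the third week of cycle 4"; two further MK-3475 cycles follow. Section 5.2.1.2 puts BCG at Weeks 7 to 12.
- **Primary analysis.** Section 10.1: "the proportion of patients with each AE will be reported along with the NCI CTCAE Grade of the AE". It names no onset period, drug, relatedness or denominator. The same paragraph does give time points for the questionnaires.
- **Attribution.** Section 8.1.2.2 requires causality and action taken to be characterised with respect to trial treatment. Table 2, titled Trial Treatment, lists both drugs. Table 8 (Section 9.1.4) puts one causality question about 'Merck product', and its action-taken item is "Did the adverse event cause Merck product to be discontinued". The term is not defined.
- **BCG supply.** Section 5.2.1.1 says "the BCG will be provided by MERCK due to the BCG shortage to ensure completion of the study". The text under Table 2 calls the supply commercial, and Section 11.1 says "BCG will be supplied through commercial sources".
- **Timing data.** Table 8 requires start and stop dates for each event.

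**The concern.** In a combination-safety trial the reader wants to know which events the investigators ascribed to which drug, and when the events began relative to the second drug. The plan has a gap on each.

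Attribution is the more serious gap, because it cannot be filled later from other data. The toxicities overlap. Section 5.2.1.4 lists hepatitis, hepatic granuloma and pneumonitis for BCG, while Table 3 covers raised liver tests and pneumonitis for MK-3475. The hold rules for the two drugs differ, and both use the term drug-related: Section 5.2.1.1.3 for Grade 4 haematological events, Table 3 throughout. A pneumonitis in Week 10 could matter to either rule, yet the form offers one undivided answer.

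The timing gap is a matter of reporting. Loss before BCG is foreseeable. Section 5.2.4 takes a subject off the trial when one drug is held for more than 2 weeks for toxicity, and Section 5.7 does not replace anyone who has started MK-3475. Such a subject counts among the 15 without having received BCG.

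**Working it through.** **1. Schedule.** Inputs are from Sections 8.1.2 and 5.2.1.2 and the flow chart.
- Course: 6 × 3 = 18 weeks, so therapy ends at Week 19. This matches Section 8.1.6.2.1.
- Weeks with BCG: 6/18 = 33%. Weeks without BCG dosing: 12/18 = 67%. Weeks before any on-study BCG: 6/18 = 33%.
- First BCG is on Day 6 × 7 + 1 = 43. Last BCG is on Day 11 × 7 + 1 = 78. Last infusion is on Day 15 × 7 + 1 = 106. The AE window closes on Day 106 + 30 = 136.
- Weeks 7-12 make up 42/136 = 31% of the window from Day 1. The stretch from first BCG onward is (136 − 42)/136 = 94/136 = 69%.

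**2. What Table 8 records under each reading of 'Merck product'.**

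| Investigator's view of cause | Term means MK-3475 | Term covers both drugs |
|---|---|---|
| MK-3475 only | Yes | Yes |
| BCG only | No | Yes |
| Both contribute | Yes or No, by judgement | Yes |
| Neither | No | No |

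On the first reading BCG is one of the other drugs or vaccines that Table 8 treats as an alternative cause, so 'BCG only' looks the same as 'neither'. On the second reading three different causes share one answer. No cell isolates BCG, and the action-taken item has the same defect.

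**3. Denominator (assumed counts).** Suppose 4 BCG-exposed subjects have a given event and 0 to 3 of the 15 leave before Week 7. The whole-course figure is 4/15 = 26.7% throughout. Among BCG-exposed subjects it is 4/15 = 26.7%, 4/14 = 28.6%, 4/13 = 30.8% or 4/12 = 33.3%. If 3 other subjects had the same event only in the lead-in, the whole-course figure becomes 7/15 = 46.7%.

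**4. What an onset split adds (assumed risks, independent six-week blocks).** Whole-course risk = 1 − (1 − p without BCG)² × (1 − p with BCG).
- 10% in every block: 1 − 0.9² × 0.9 = 27.1%, or 4.1 of 15 subjects.
- 10% without BCG and 30% with it: 1 − 0.9² × 0.7 = 43.3%, or 6.5 of 15. With 20% or 40% in the BCG block the result is 35.2% or 51.4%.
- Exact 95% intervals overlap heavily: 4/15 gives 7.8-55.1%, 6/15 gives 16.3-67.7%.
- A split table would show expected counts, lead-in against BCG block, of 1.5 and 1.5 in the first case and 1.5 and 4.5 in the second.
- The split is not a test. Exact McNemar power with 15 subjects is 9% for 10% against 30%, and 26% for 10% against 40%.

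**The case against.** A reader might infer that the primary result cannot show combination toxicity at all. The documents do not support that. Start and stop dates are recorded, AEs are reviewed at each visit, and the diary carries each BCG treatment date. Any event can be placed relative to BCG. The split is simply not planned, and even the absence of a split is read from the silence of Section 10.1.

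A reader might also infer that two thirds of the course is MK-3475 alone. That is true only of dosing weeks. Weeks 13-18 follow combined exposure, and Section 5.2.3.3 says MK-3475 events may appear months after the last dose. Only Weeks 1-6 are BCG-naive on study.

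The whole-course proportion is also a proper primary summary. Section 4.2.1 gives the lead-in a purpose, priming the bladder, so it belongs to the regimen. A subject who leaves during it for toxicity is a failure to deliver that regimen. This stands, and the whole-course table should stay. Nor is the lead-in a clean within-subject reference: period is confounded with cumulative MK-3475 exposure, and later periods contain only those who continued.

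On attribution, the best defence is that 'Merck product' naturally means MK-3475. Table 9 lists nothing else as supplied by Merck, and Table 8 alternates the term with 'test drug'. That is plausible, but it selects the reading under which BCG-caused events are marked unrelated. It is also true that most BCG hold triggers, such as fever and haematuria, need no attribution, which limits the operational effect. Section 8.1.2.2 does ask about trial treatment generally, but Table 8 provides no BCG entry to meet that request. The CRF itself is not in the documents, so it may capture more.

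**Conclusion.** The attribution gap holds on either reading of the term. As specified, no event can be ascribed specifically to BCG in a trial whose primary question is the safety of MK-3475 with BCG, and onset dates cannot supply that judgement. This rests on Table 8 reflecting what the CRF collects.

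The timing gap holds in a limited form. Section 10.1 specifies only whole-course proportions. They are valid for the full regimen but silent on whether events came before, during or after BCG, and they include in the denominator subjects who never reached Week 7. The size of the effect depends on counts the documents do not give. In the assumed examples the denominator alone moves a rate from 26.7% to at most 33.3%, which is small beside the exact interval for 4/15. The split therefore helps to describe events. It cannot establish what BCG adds. The changes are worth making, but nothing here invalidates the planned table.

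**What to change.** 1. **Attribution.** In Table 8 and the AE CRF, replace 'Merck product' with separate causality and action-taken entries for MK-3475 and for BCG, allowing both to be marked. Split earlier entries retrospectively where source notes allow, and flag the rest. Reconcile Section 5.2.1.1 with the text under Table 2 and Section 11.1 on who supplies BCG.
2. **Timing.** In Section 10.1, keep the whole-course table and add one descriptive table by onset: (a) first MK-3475 dose until just before the first BCG instillation; (b) first BCG until 30 days after the last BCG; (c) later. Defining (a) by the actual first instillation leaves no gap if BCG is delayed. On schedule, (b) runs from Day 43 to Day 108, which is 66 days. Use subjects entering each period as denominators, with at least one instillation required for (b).
3. **Interpretation.** State that the split is descriptive only: 15 subjects, no control, and period confounded with cumulative MK-3475 exposure and delayed events.

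The cost is one more table from dates already collected, extra CRF fields, small denominators, and the work of flagging earlier causality entries. No new visits or subjects are needed. Fixing the windows in advance also avoids choosing them after the events are known.
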